Nanoliposomal irinotecan will be administered by IV infusion over approximately 90 minutes. One cycle is 14 days, subsequent doses should be administered on the first day of each cycle +/- 3 days. An additional 1 day is provided for a holiday.

Three patients will be accrued to level 1. If no dose limiting toxicities are observed following completion of 4 weeks (2 cycles) of treatment then accrual to dose level 2 will proceed (patients must be evaluated prior to their cycle 3 treatment and this will be used to confirm DLTs). If a DLT is observed in one of the first 3 patients in a dose level, then accrual for that level will be expanded to 6 patients. Accrual will continue in this way until the MTD of nanoliposomal irinotecan with temozolomide 50mg/m²/day is determined. Two or more instances of DLT in a cohort of 6 patients will result in the preceding dose level being defined as the MTD. If two or more instances of DLT in a cohort of 6 patients occurs in dose level 1 then dose level -1 of nanoliposomal irinotecan will be investigated. After determination of the MTD, the final cohort will be expanded so that a total of 25 patients are treated on study. The final cohort will be treated at the MTD.

If a patient is unable to receive 4 weeks of treatment (2 cycles) for reasons other than dose limiting toxicity, they will be replaced in a cohort.

Premedication

All patients must be premedicated prior to nanoliposomal irinotecan infusion with standard doses of dexamethasone and a 5-HT3 antagonist or other anti-emetics as per standard institutional practices for irinotecan administration. Atropine may be prescribed prophylactically for patients who experienced acute cholinergic symptoms in previous cycles.

Premedication prior to temozolomide is not required and may be administered as per institutional standard of care.

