5.1 Treatment Delay

A new course of treatment (cycle) with nanoliposomal irinotecan and temozolomide should not begin until the following criteria are met.

- Platelets $\geq 100,000 \times 10^9/L$ (100,000/mm³)
- Granulocytes (ANC) $\geq 1.5 \times 10^9/L$ (1,500/mm³)
- Recovery from other clinically significant, treatment related non-hematologic toxicities to \leq Grade 2

*please refer to section 5.2 for events that require dose reductions cycles 3-on*The treating physician may decide to hold treatment secondary to other toxicities even if deemed not related to treatment if the physician feels it is in the patient's best interest. This must be documented and submitted to BrUOG on treatment form and AE log.

If the patient does not meet these criteria at the start of a scheduled cycle, treatment should be delayed until these requirements are met.

Patients who require a treatment delay of more than 4 weeks due to toxicity will be removed from protocol treatment. Patients who require a treatment delay of more than 8 weeks not due to toxicity will be removed from protocol treatment.

If a patient is unable to receive 4 weeks of treatment (2 cycles) for reasons other than a dose limiting toxicity, they will be replaced in a cohort.

5.2 Definition of Dose Limiting Toxicities:

Dose limiting toxicities will be defined as the following toxicities occurring during the first 2 cycles (28 days) of therapies. If however a patient experiences one of the below toxicities after cycle 2 they will be dose reduced (both drugs), even though it will no longer be defined as a DLT.

- Grade 4 neutropenia (ANC < 500/mm³) for > 7 days
- ANC < 1000/mm³ with fever or infection
- Platelets < 25,000/mm³
- Platelets < 50,000/mm³ requiring transfusion
- Grade 3 or 4 treatment related non-hematologic toxicities excluding alopecia.
 - Grade 3 nausea, vomiting or diarrhea will only be considered a dose limiting toxicity if it occurs for greater than 72 hours despite maximal medical support.
 - Grade 3 electrolyte abnormalities will not be considered dose limiting toxicities if the electrolyte disorder can be corrected to grade 2 or less within 72 hours.
 - A grade 4 electrolyte abnormality will be considered a DLT.
- Delay of treatment for > 2 weeks due to toxicity (do not score a second DLT for a treatment delay caused by the same event)

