^C It is appropriate to use labs from screening for cycle 1 day 1, if labs are within 14 days (pregnancy must be within 7 days of drug day 1 as noted above for applicable patients). A physical exam within 7 days prior to cycle 1 day 1 may be utilized. Weight, vitals, PS, AE and conmed assessment can be used from screening for cycle 1 day 1 if within 14 days. Labs and physical exam (with weight, vitals, PS and AEs) for all subsequent cycles can be within 3 days prior to day 1 of treatment cycle (another 1 day is given for holiday).

^D- For patients removed from protocol treatment due to toxicity(or other reason), without progression, follow-up until disease progression will include brain MRI, disease free and overall survival and physical approximately every 3 months (+/- 1 month). For patients who come off study for progression, overall survival is to be reported approximately every 3months (+/- 1 month). Follow-up will be for 2 years.

^E post-menopausal women (surgical menopause or lack of menses \geq 12 months) do not need to have a pregnancy test, document status

^F Adverse event evaluation, inclusive of SAE evaluation, and Performance status assessment will be done 30 days (+1 week) post last dose of drug . SAEs occurring outside this 30 day window must be reported if the event is considered to be possibly related to the study drug. If a patient begins a new treatment, AE evaluation will be stopped unless the patient experiences an event that is thought to be possibly related to the study drug. SAE evaluation will not be stopped if patient begins a new treatment.

^G Physical and performance status assessment to be done in coordination with 30 day toxicity assessment (+ 1 week allowed).

^H MRI of brain with contrast to be done every 2 months (approximately after every 4 cycles) +1 month window.. More frequent MRI imaging is allowed per treating MD but all information must be sent to BrUOG.

7.0 RESPONSE ASSESSMENT:

7.1 Response Definition:

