Nanoliposomal irinotecan will be administered by IV infusion over approximately 90 minutes (this time frame may be extended secondary to an infusion reaction and as per information in section 5.4) as per the dose level the patient was assigned at the time of registration and until disease progression or withdrawal

Cycle duration is 2 weeks. The first cycle Day 1 is a fixed day; subsequent doses should be administered on the first day of each cycle +/- 3 days (an additional day is given for a holiday).

Prior to administration, the appropriate dose of nanoliposomal irinotecan must be diluted in 5% Dextrose Injection solution (D5W) to a final volume of 500mL. Care should be taken not to use in-line filters or any diluents other than D5W. Nanoliposomal irinotecan can be administered using standard PVC-containing intravenous administration bags and tubing.

The actual dose of nanoliposomal irinotecan to be administered will be determined by baseline calculation of the patient’s body surface area. Dose only needs to be re-calculated if there is a 10% change in weight or at the discretion of the treating MD. A +/- 5% variance in the calculated total dose will be allowed for ease of dose administration. Since nanoliposomal irinotecan vials are single-use vials, site staff must not store any unused portion of a vial for future use and they must discard unused portions of the product.

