17.0 STATISTICS

SAMPLE SIZE AND STATISTICAL DESIGN

Three patients will be accrued to level 1. If no dose limiting toxicities are observed following completion

7/21/16, 7/26/16, 8/1/16, 8/2/16, 8/3/16, 8/4/16, 8/9/16, 8/15/16, 8/16/16, 8/17/16 submitted Merrimack, 10/3/16 Merrimack edits, 10/7/16. 32
Re-submitted Merrimack 10/11/16, 11/15/16 from Merrimack, 11/17/16, 11/30/16 back to Merrimack, approved Merrimack 1/5/17,
1/26/17, 2/7/17 company review, 2/8/17, 2/13/17, 3/2/17 company, 3/3/17, approved company 3/23/17, RN/Pharmacy/EXEC review
3/31/17, 3/31/17 BrUOG, to company 4/6/17, Ipsen 4/18/17, BrUOG 4/20/17, Ipsen approved 5-4-17, FDA 5-5-17, FDA IND exemption
5/18/17, Protocol change 5/18/17, Protocol change 7/10/17 with IB v10, 8/17/17, Amendment # 1 4/6/18, Amendment #2 8/14/18,
Amendment # 3 12/8/18

of 4 weeks of treatment (2 cycles) then accrual to dose level 2 will proceed. If a DLT is observed in one of the first 3 patients in a dose level, then accrual for that level will be expanded to 6 patients. Accrual will continue in this way until the MTD is determined. Two or more instances of DLT in a cohort of 6 patients will result in the preceding dose level being defined as the MTD. After determination of the MTD, the final cohort will be expanded so that a total of 25 patients are treated on study. The final cohort will be treated at the MTD.

If a patient is unable to receive 4 weeks of treatment (2 cycles) for reasons other than a dose limiting toxicity, they will be replaced in a cohort. Patients who require a treatment delay of more than 8 weeks not due to toxicity will be removed from protocol treatment.

If two or more instances of DLT in a cohort of 6 patients occurs in dose level 1 then dose level -1 of nanoliposomal irinotecan will be investigated.

Definition of Dose Limiting Toxicities

- Grade 4 neutropenia (ANC < 500/mm³)
- ANC <1000/mm³ with fever (temp > 101) or infection
- Grade 4 thrombocytopenia: Platelets <25,000/mm³
- Platelets <50,000/mm³ requiring transfusion
- Grade 3 or 4 treatment related non-hematologic toxicities excluding alopecia.
 - Grade 3 nausea, vomiting or diarrhea will only be considered a dose limiting toxicity if it occurs for greater than 72 hours despite maximal medical support.
 - Grade 3 electrolyte abnormalities will not be considered dose limiting toxicities if the electrolyte disorder can be corrected to grade 2 or less within 72 hours.
 - A grade 4 electrolyte abnormality will be considered a DLT.

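### The evaluation that confirms DLTs may fall on day 23, so up to 5 of the 28 DLT days need not be covered by any required check before the next dose level opens.

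*Combined protocol and SAP*

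**What the plan says.** Four expressions mark the end of the DLT period, and the plan treats them as one time point.

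- **DLT definition (5.2):** "toxicities occurring during the first 2 cycles (28 days) of therapies". The same section says that a listed toxicity arising after cycle 2 leads to dose reduction but no longer counts as a DLT.
- **Escalation rule (4.0, repeated in 17.0):** if no DLT is seen following completion "of 4 weeks of treatment (2 cycles) then accrual to dose level 2 will proceed".
- **Confirming check (4.0 only, in parentheses after the escalation rule):** "patients must be evaluated prior to their cycle 3 treatment and this will be used to confirm DLTs".

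Two windows bear on when that check takes place.

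- **Dosing (4.0):** "One cycle is 14 days, subsequent doses should be administered on the first day of each cycle +/- 3 days", and "An additional 1 day is provided for a holiday". The administration text in section 9.1.3 adds: "The first cycle Day 1 is a fixed day".
- **Assessment (6.0, footnote C):** for cycles after the first, laboratory tests and the physical examination with adverse event review "can be within 3 days prior to day 1 of treatment cycle (another 1 day is given for holiday".

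The calendar in 6.0 schedules blood counts before each cycle and off study, with none in mid-cycle. Nothing sets an earliest day for the confirming evaluation or asks for a second DLT review before a level is cleared.

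**The concern.** With every dose and visit on its nominal day, 2 cycles, 4 weeks, 28 days and the visit before cycle 3 nearly coincide. The permitted windows pull them apart, and the plan does not say which then governs.

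Two things follow. First, the check used to confirm DLTs can be completed while part of the DLT window is still to come. Some DLTs in 5.2 are laboratory findings, such as platelets below 25,000/mm³, and can be silent. After an early blood draw before cycle 3, the next scheduled count is the one before cycle 4. Second, if cycle 3 starts early, an event in the last days of the 28 may be filed as occurring after cycle 2, when 5.2 no longer calls it a DLT.

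Each escalation decision rests on three to six patients, so one event that is unknown at the decision, or filed under the wrong cycle, can change it.

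**Working it through.** **1. Reproduce the stated window.** 2 cycles × 14 days = 28 days, so nominal cycle 3 day 1 is day 29. This agrees with 5.2.

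**2. Earliest confirming evaluation, counted from the fixed cycle 1 day 1.** The evaluation day is taken as observed, so days not covered = 28 − evaluation day.

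| Situation | Cycle 3 dose | Earliest evaluation | Days not covered |
|---|---|---|---|
| Cycle 3 at its earliest | 29 − 3 = 26 | 26 − 3 = 23 | 28 − 23 = 5 (18%) |
| Cycle 3 on time | 29 | 29 − 3 = 26 | 28 − 26 = 2 |
| Cycle 3 on time, evaluated the same day | 29 | 29 | 0 |

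Holiday days are left out. If both could be used in the early direction, which the text does not say, the first row becomes dose day 25, evaluation day 21, and 7 days not covered. In the on-time row, one holiday day on the assessment makes it day 25 and 3 days.

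**3. Next scheduled blood count.** Nominal cycle 4 is day 29 + 14 = 43. Its earliest pre-cycle assessment is 43 − 3 − 3 = day 37, well after day 28.

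**4. Classification.** With cycle 3 given on day 26, an event on days 26 to 28 is within 28 days of the start. If cycle 2 is taken to end when cycle 3 is dosed, the event is after cycle 2. The two halves of the 5.2 definition then disagree.

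**5. Illustrative effect on a cohort decision.** The documents give no DLT onset pattern or expected DLT rate. Assume a constant hazard and a true 28-day risk p = 0.30, and suppose that events after the evaluation are not known at the decision. A level clears with no DLT in the first three patients, or with one in the first three and none in the next three.

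- Full 28 days: 0.7³ + 3(0.3)(0.7²)(0.7³) = 0.343 + 0.151 = **0.49**.
- Risk captured by day 23: 1 − 0.7^(23/28) = 0.254, so the chance of no event is 0.746.
- Only the last patient in each group of three is evaluated on day 23:
  - P(0 of 3) = 0.7² × 0.746 = 0.366
  - P(1 of 3) = 2(0.3)(0.7)(0.746) + 0.7²(0.254) = 0.438
  - P(clear) = 0.366 + 0.438 × 0.366 = **0.53**
- All patients evaluated on day 23: 0.746³ + 3(0.254)(0.746⁵) = **0.59**.

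The same steps with p = 0.40 give 0.31 for full observation, 0.34 with only the last patient in each group early, and 0.41 with all early.

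**The case against.** The strongest reply is that the visit is an added requirement, not a substitute. It sits in parentheses beside a rule that already demands completion of 4 weeks, and section 17 repeats that rule. A reader might infer from the visit windows that a level can be cleared before day 28. The documents do not support that as a general statement: read as calendar weeks, 4 weeks must have passed before the next level opens. This part of the reply stands. What it leaves open is coverage. A level could open on day 29 on the strength of an evaluation made on day 23.

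Second, a DLT is defined by when it occurs, not by when it is confirmed. Section 5.2 (Example 2) has a DLT recognised on day 5, away from a pre-cycle visit, and section 11 records adverse events throughout the trial. A symptomatic event on day 25 would therefore probably be reported and still meet the definition. This also stands, and it means that a systematic undercount of DLTs, or an MTD that is necessarily too high, does not follow from the text. It does not help with a silent laboratory DLT, and no one is required to review events through day 28 before escalating.

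Third, the cycle is fixed at 14 days, so early dosing need not shorten it. On that reading cycle 2 ends on day 28 and the conflict in step 4 disappears. The reading is reasonable, but the plan does not state it. The same point weakens a tempting day-20 figure, which needs two successive early doses and windows re-counted from each actual dose. No section provides for that, and the fixed cycle 1 day 1 points the other way.

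Finally, a cohort decision waits for the last patient, and patients who started earlier have usually passed day 28. The 0.59 is therefore a bound, not an expectation.

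**Conclusion.** The point holds as a gap in coverage and an inconsistency of terms. The required DLT check can fall on day 23, leaving up to 5 of the 28 days outside it. With on-time dosing the figure is 0 to 2 days, or 3 if a holiday day is used for the assessment. No later DLT review or blood count is required before the next level opens, and an event on days 26 to 28 after an early cycle 3 can be classified either way.

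The effect is probably modest. At an assumed 30% risk the chance of clearing a level moves from 0.49 to about 0.53 in the more realistic case, with 0.59 as the ceiling. These figures rest on a constant hazard and on late events being unknown at the decision; the documents support neither assumption directly. The day-23 result needs only the stated windows and the fixed cycle 1 day 1. The point does not show that levels will be cleared before 4 weeks have passed or that the MTD will be biased upward.

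**What to change.** Reconcile 2 cycles, 4 weeks, 28 days and the evaluation before cycle 3 in sections 4.0, 5.2 and 17, so that one stated period governs DLT scoring and the escalation decision when doses are early or late. Add that the next level opens only once every patient in the cohort has a documented toxicity review covering the full stated DLT window, through day 28. The plan should also say whether that review needs a blood count for patients whose draw before cycle 3 was early, since some DLTs are laboratory values.

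Scoring need not run on to a delayed evaluation before cycle 3, which would create a new DLT window. The dosing windows and the DLT criteria stay unchanged. The cost is amendment wording, a short extra check for patients evaluated early, and a delay of a few days to a cohort decision.

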5.0 TOXICITIES, DOSE MODIFICATIONS, AND MANAGEMENT

Toxicities will be recorded as adverse events on the Adverse Event case report form and must be graded using The National Cancer Institute's Common Toxicity Criteria (CTCAE) version 4.03 (Appendix C).

5.1 Treatment Delay

A new course of treatment (cycle) with nanoliposomal irinotecan and temozolomide should not begin until the following criteria are met.

- Platelets $\geq 100,000 \times 10^9/L$ (100,000/mm³)
- Granulocytes (ANC) $\geq 1.5 \times 10^9/L$ (1,500/mm³)
- Recovery from other clinically significant, treatment related non-hematologic toxicities to \leq Grade 2

*please refer to section 5.2 for events that require dose reductions cycles 3-on*The treating physician may decide to hold treatment secondary to other toxicities even if deemed not related to treatment if the physician feels it is in the patient's best interest. This must be documented and submitted to BrUOG on treatment form and AE log.

If the patient does not meet these criteria at the start of a scheduled cycle, treatment should be delayed until these requirements are met.

Patients who require a treatment delay of more than 4 weeks due to toxicity will be removed from protocol treatment. Patients who require a treatment delay of more than 8 weeks not due to toxicity will be removed from protocol treatment.

If a patient is unable to receive 4 weeks of treatment (2 cycles) for reasons other than a dose limiting toxicity, they will be replaced in a cohort.

5.2 Definition of Dose Limiting Toxicities:

Dose limiting toxicities will be defined as the following toxicities occurring during the first 2 cycles (28 days) of therapies. If however a patient experiences one of the below toxicities after cycle 2 they will be dose reduced (both drugs), even though it will no longer be defined as a DLT.

- Grade 4 neutropenia (ANC < 500/mm³) for > 7 days
- ANC < 1000/mm³ with fever or infection
- Platelets < 25,000/mm³
- Platelets < 50,000/mm³ requiring transfusion
- Grade 3 or 4 treatment related non-hematologic toxicities excluding alopecia.
 - Grade 3 nausea, vomiting or diarrhea will only be considered a dose limiting toxicity if it occurs for greater than 72 hours despite maximal medical support.
 - Grade 3 electrolyte abnormalities will not be considered dose limiting toxicities if the electrolyte disorder can be corrected to grade 2 or less within 72 hours.
 - A grade 4 electrolyte abnormality will be considered a DLT.
- Delay of treatment for > 2 weeks due to toxicity (do not score a second DLT for a treatment delay caused by the same event)

Patients can resume treatment post a dose limiting toxicity (with a dose level reduction to both drugs), once they have recovered from treatment related non-hematologic toxicities to \leq grade 2 and their platelets count is $\geq 100,000 \times 10^9/L$ (100,000/mm³) and their ANC count is $\geq 1.5 \times 10^9/L$ (1,500/mm³). A patient is required to be removed from protocol treatment if treatment is held in cycles 1 or 2 for a DLT > 4 weeks. Patient's removed from treatment for this reason would undergo off study assessments, followed by 30 day assessments and would be followed as per section 6.

Of note when a patient experiences a DLT both drugs must be held and then both must be reduced, but they may be reduced at different times if a patient is found to experience a DLT mid-cycle. If this occurs, the TMZ will be held until patient's toxicities resolve to criteria above, after-which the dose of TMZ will be reduced for the remainder of the cycle and then at the start of the next cycle the nanoliposomal irinotecan will be reduced.

Example 1: If prior to day 1 of a cycle a patient experiences a DLT, dosing will be held until criteria for treatment are met. Both drugs will then be reduced.

Example 2: If a patient meets dosing criteria day 1 the cycle will begin and patient will be treated day 1 with both drugs. Since TMZ is given on a continuous basis if a patient experiences a DLT on day 5 TMZ will be held until patient meets criteria for treatment and then TMZ will be dose reduced for the remainder of the cycle. Nanoliposomal irinotecan will be dose reduced at the next cycle.

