3.1.5 Life expectancy >12 weeks as noted by treating investigator

3.1.6 Laboratory results requirements

- Absolute neutrophil count (ANC) $\geq 1500/\text{mm}^3$.
- Platelets (Plt) $\geq 100,000/\text{mm}^3$
- Hemoglobin (Hgb) $\geq 9.0 \text{ g/dL}$
- Total bilirubin $\leq 1x \text{ ULN}$
- Albumin levels $\geq 3.0 \text{ g/dL}$
- Aspartate aminotransferase (AST) and alanine aminotransferase (ALT) $\leq 2.5 \times \text{ ULN}$
- Serum creatinine $\leq 1.5 \times \text{ ULN}$

3.1.7 . Not pregnant and not nursing. Women of child bearing potential must have a negative serum pregnancy test (minimum sensitivity 25 IU/L or equivalent units of HCG) within 7 days prior to Day 1 of treatment. Post-menopausal women (surgical menopause or lack of menses ≥ 12 months) do not need to have a pregnancy test, please document status.

3.1.8. Confirmation of informed consent.

3.1.9 . Men and women of childbearing potential enrolled in this study must agree to use adequate barrier birth control measures during the course of the study and for at least 2 months after the last treatment on study.

3.1.10 Recovered (\leq grade 1) from clinically significant effects of any prior surgery, radiotherapy or other anti-neoplastic therapy, except alopecia or hematological laboratory values (see 3.1.6 for required values for the trial).

3.1.11 Stable corticosteroid dose at least 7 days prior to day 1

3.1.12 Patient must have assessable (measurable) disease at baseline by brain MRI. Must be contrast enhancing. The tumor size will be measured in millimeters and is the largest cross-sectional area using perpendicular measurements of contrast enhancing abnormality.

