5.3 Dose Modifications

Dose limiting toxicities are defined in the first two cycles of treatment. Patients experiencing a toxicity defined above in section 5.2 at any time on protocol treatment, will have a 1 dose level reduction of nanoliposomal irinotecan **and** temozolomide. Patients experiencing a second dose limiting toxicity will be removed from protocol treatment.

For patients whose treatment is held for grade 3 or 4 non-hematologic adverse events not related to treatment (which would be at treating physician's discretion and not required per study), dose reductions are not required when treatment is resumed.

Patients can resume treatment once they have recovered from other clinically significant, treatment related non-hematologic toxicities to \leq Grade 2, their platelets count is $\geq 100,000 \times 10^9/L$ (100,000/mm 3) and their ANC count is $\geq 1.5 \times 10^9/L$ (1,500/mm 3). Patients can resume treatment post a dose limiting toxicity (with a dose level reduction to both drugs), once they have recovered from treatment related non-hematologic toxicities to \leq grade 2 and their platelets count is $\geq 100,000 \times 10^9/L$ (100,000/mm 3) and their ANC count is $\geq 1.5 \times 10^9/L$ (1,500/mm 3). A patient is required to be removed from protocol treatment if treatment is held in cycles 1 or 2 for a DLT >4 weeks. Patient's removed from treatment for this reason would undergo off study assessments, followed by 30 day assessments and would be followed as per section 6.

If a patient experiences an event outlined in 5.2 after cycle 2, they will need to be dose reduced (both drugs), even though it will no longer be defined as a DLT.

Treatment:

Nanoliposomal irinotecan 1 cycle = 14 days

	Dose Level -1	Dose Level 1	Dose Level 2	Dose Level 3
Nanoliposomal irinotecan	43 mg/m 2 , day 1	50 mg/m 2 , day 1	70 mg/m 2 , day 1	80 mg/m 2 , day 1

Temozolomide: Daily x 14 days = 1 cycle

	Dose Level -1	Dose Level 1 (Starting dose level all)
Temozolomide	25mg/m 2 /day	50mg/m 2 /day

Patients who require more than one dose reduction will be removed from protocol treatment.

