APPENDIX B: Checklist

Onivyde (nanoliposomal irinotecan) and Metronomic Temozolomide for Patients With Recurrent Glioblastoma: A Phase IB/IIA Brown University Oncology Research Group Study

Inclusion Criteria

(y/n) Histologically confirmed glioblastoma multiforme or gliosarcoma

(y/n) Progression after at least one line of therapy.

(y/n) Patient must have received temozolomide and radiation but it is not required that they were given concurrently.

(y/n) Voluntary, informed consent, Date signed _____

(y/n) Age \geq 18

(y/n) All males and women of childbearing potential, must be willing to consent to use an adequate barrier birth control measure while on treatment and for at least 2 months after the last treatment on study

(y/n) Brain MRI completed with contrast

(y/n) Patient must be able to tolerate brain MRI with contrast

(y/n) EKG within 8 weeks study entry

(y/n) Life expectancy >12 weeks as noted by treating investigator

(y/n) Absolute neutrophil count $\geq 1,500/\mu\text{L}$, Date _____

(y/n) Platelet $\geq 100,000/\mu\text{L}$, Date _____

(y/n) Total bilirubin $\leq 1.0 \times \text{ULN}$, Date _____

(y/n) AST $\leq 2.5 \times \text{ULN}$ and ALT $\leq 2.5 \times \text{ULN}$ Institution

(y/n) Creatinine $\leq 1.5 \times \text{ULN}$

(y/n) HGB $\geq 9.0\text{g/dL}$

(y/n) Albumin levels $\geq 3.0 \text{ g/dL}$

(y/n) Karnofsky performance score ≥ 60

(y/n) Recovered (\leq grade 1) from the effects of any prior surgery, radiotherapy or other anti-neoplastic therapy, except alopecia. See section 3.1.10

(y/n) Stable corticosteroid dose at least 7 days prior to day 1

 (y/n) Patients must have assessable (measurable) disease at baseline by brain MRI. Must be contrast enhancing. The tumor size will be measured in millimeters and is the largest cross-sectional area using perpendicular measurements of contrast enhancing abnormality.

Exclusion Criteria:

 (y/n) Non-GBM primary invasive malignant neoplasm that is considered by treating investigator to likely cause death in the next 5 years.

 (y/n) Patient not to be receiving any cancer therapy or investigational anti-cancer drug.

 (y/n) Radiation therapy or cytotoxic chemotherapy or biologics or immunotherapy within previous three weeks from day 1 of drug (no anticancer treatment of any kind within 3 weeks of day 1 of drug).

 (y/n) Evidence of an active infection requiring intravenous antibiotic therapy

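### The platelet threshold for starting or resuming treatment is 1000 times too high in its 10^9/L form, at four places in sections 5.1 to 5.3

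*Combined protocol and SAP*

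**What the plan says.** Section 5.1 lists what must be met before a new cycle of both drugs begins. The platelet line reads "Platelets $\geq 100,000 \times 10^9/L$ (100,000/mm³"). The line below it gives the neutrophil requirement as "Granulocytes (ANC) $\geq 1.5 \times 10^9/L$ (1,500/mm³"). A patient who does not meet the criteria on the scheduled day waits until they are met.

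The platelet pair is repeated wherever the protocol says when treatment may resume:

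- Section 5.2, resuming after a DLT: "their platelets count is $\geq 100,000 \times 10^9/L$ (100,000/mm³").
- Section 5.3, resuming in general: "Grade 2, their platelets count is $\geq 100,000 \times 10^9/L$ (100,000/mm 3").
- Section 5.3, resuming after a DLT: "grade 2 and their platelets count is $\geq 100,000 \times 10^9/L$ (100,000/mm 3").

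Other parts of the document state platelet limits in one unit only. Section 3.1.6 requires "Platelets (Plt) $\geq 100,000/\text{mm}^3" at entry, and the Appendix B checklist has "Platelet $\geq 100,000/\mu\text{L". The DLT definition in section 17.0 includes "Grade 4 thrombocytopenia: Platelets <25,000/mm³". Sections 5.2 and 17.0 both also count a platelet level below 50,000/mm³ that needs transfusion.

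**The concern.** A threshold stated in two units should be the same quantity in both. Here the two forms differ, and the form printed first is the wrong one. These lines decide whether a patient is dosed. After cycle 1 they are the only platelet criterion for going ahead; for cycle 1 the entry criterion also applies.

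Taken literally, the 10^9/L form would hold patients whom the bracketed form allows to be treated. A site whose laboratory reports in 10^9/L would look to that form first. The wrong figure could also be carried into order sets, case report form checks or monitoring checklists.

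**Working it through.** **Inputs.** The platelet pair in 5.1, 5.2 and 5.3 is 100,000 x 10^9/L and 100,000/mm³. The neutrophil pair in 5.1 is 1.5 x 10^9/L and 1,500/mm³. Entry requires 100,000/mm³ (3.1.6) or 100,000/µL (Appendix B). The DLT cut-offs are 25,000 and 50,000/mm³ (5.2 and 17.0).

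**Formula.** 1 L = 10^6 mm³, so count per L = count per mm³ x 10^6. It follows that 1 x 10^9/L = 1,000/mm³. Also, 1 µL = 1 mm³.

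**Neutrophils, as a check of the method.** 1,500/mm³ x 10^6 = 1.5 x 10^9/L. This reproduces the protocol's pair.

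**Platelets.**

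| Starting form | Per litre | In 10^9/L | Per mm³ |
|---|---|---|---|
| Bracketed value, 100,000/mm³ | 1 x 10^11 | 100 | 100,000 |
| Printed 100,000 x 10^9/L | 1 x 10^14 | 100,000 | 100,000,000 |

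Ratio: 10^14 / 10^11 = 1000. The platelet pair is not reproduced.

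**Which form is intended.** The entry criterion and the checklist are both 100 x 10^9/L once converted. The DLT cut-offs are 25 and 50 x 10^9/L. A threshold of 100 x 10^9/L equals the entry value and lies above both cut-offs on the same scale. A threshold of 100,000 x 10^9/L is 1000 times the entry value and fits none of them.

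**Corrected pair.** 100 x 10^9/L = 10^11/L, and 10^11 / 10^6 = 100,000/mm³, which agrees exactly with the bracket.

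**Direction of the error.** A count below 100,000/mm³ fails both forms. A count from 100,000/mm³ up to just under 100,000,000/mm³ passes the bracketed form and fails the other. The misprint can only add holds; it cannot release a patient who should be held.

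**Places.** 5.1 (1) + 5.2 (1) + 5.3 (2) = 4.

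**The case against.** The strongest reply is that this is proofreading. Every occurrence carries the correct value in brackets, that value is used consistently elsewhere, and no patient could meet the 10^9/L figure. A site would see the slip and work to 100,000/mm³. The error also runs in the safe direction. All of this stands, and it is why the point is minor. It does not make the line correct: a dosing criterion should be right in each unit it states.

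One could ask whether a literal reading would disturb the trial's counting rules. A delay of more than 2 weeks is a DLT only if toxicity caused it, and the 4-week removal rule in 5.1 has the same condition. A hold caused by the misprint alone would trigger neither. Other rules could in principle be reached: removal when a hold for a DLT in cycles 1 or 2 lasts more than 4 weeks (5.2 and 5.3), removal after more than 8 weeks' delay not due to toxicity, and replacement of a patient who does not complete two cycles for non-DLT reasons. These need a reading that no site is likely to adopt, so they do not raise the rating.

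A last possibility is a fault in reading the PDF, since 100,000 x 10^6/L would equal 100,000/mm³. The identical form at four places, each beside a correctly read neutrophil exponent, makes that unlikely. A look at the source file would settle it.

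**Conclusion.** The point holds. The 10^9/L form of the platelet threshold is 1000 times the bracketed value, at four places in the criteria for starting and resuming treatment. The intended value is 100,000/mm³, and finding it needs no clinical judgement.

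The severity is minor. Little or no effect is expected on DLT counts, the MTD, response or survival, and no sample size, alpha or power figure uses this threshold. The conclusion on size assumes that sites apply the bracketed value. The arithmetic assumes only that the exponent was read correctly from the PDF.

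**What to change.** In the next amendment, give the platelet criterion as at least 100 x 10^9/L (100,000/mm³) at all four places: once in 5.1, once in 5.2 and twice in 5.3. Check the wording against the source file at the same time, along with any order set or case report form that copied the line. The bracketed value, 3.1.6, the Appendix B checklist and the platelet DLT cut-offs need no change on this account. The cost is a text correction, with no extra patients, procedures or analyses.
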